13.1.2 OCULAR DISCOMFORT AND DRY EYE SYMPTOMS

Ocular discomfort scores will be subjectively graded by the subjects according to the following scale, rating each eye separately: 0 = No discomfort, 1 = Intermittent awareness, 2 = Constant awareness, 3 = Intermittent discomfort, 4 = Constant discomfort. Additionally, subjects will rate the severity of each of the following symptoms, with regard to how both their eyes feel, in general – overall ocular discomfort, burning, dryness, grittiness and stinging according to the following 6-point (0 to 5) scale where 0 = none and 5 = worst. Both ocular discomfort and dry eye symptoms will be assessed at each visit.

Ocular discomfort and dry eye symptoms for the study eye will be summarized using continuous descriptive statistics by visit for each treatment group and all randomized subjects. A subject listing of ocular discomfort and 4-symptom questionnaire results will also be produced.

13.1.3 LISSAMINE GREEN STAINING (ORA CALIBRA® SCALE)

Lissamine green staining will be conducted at Visits 3, 4 (pre-CAE, post-CAE, and pre- to post-CAE), and 5 (pre-CAE, post-CAE, and pre- to post-CAE) in the following regions: central, superior, inferior, temporal, nasal, corneal sum, conjunctival sum, and total eye score.

The staining will be graded with the Ora Calibra[®] Corneal and Conjunctival Staining Scale, which is as follows: 0 = None, 1 = Trace, 2 = Mild, 3 = Moderate, 4 = Severe. Half (0.5) increments may be used.

The lissamine staining results for the study eye will be summarized using continuous descriptive statistics by visit and eye for each treatment group and all randomized subjects. A subject listing of lissamine staining results will also be produced.

13.1.4 TEAR FILM BREAK-UP TIME

TFBUT will be measured in seconds using a stopwatch and a digital image recording system for the right eye followed by the left eye at Visits 3, 4 (pre-CAE, post-CAE, and pre- to post-CAE), and 5 (pre-CAE, post-CAE, and pre- to post- CAE). For each eye, 2 measurements will be taken and averaged unless the 2 measurements are > 2 seconds apart and are each < 10 seconds, in which case, a third measurement would be taken and the 2 closest of the 3 would be averaged.

The TFBUT values for the study eye will be summarized using continuous descriptive statistics by visit and eye for each treatment group and for all randomized subjects. A subject listing of TFBUT will also be produced.

13.1.5 CONJUNCTIVAL REDNESS

The Ora Calibra® Conjunctival Redness Scale for Dry Eye will be performed at Visits 2 (pre-CAE), 3, 4 (pre-CAE, post-CAE, and pre- to post-CAE), and 5 (pre-CAE, post-CAE, and pre- to post-CAE). The scale is as follows: 0 = None, 1 = Trace, 2 = Mild, 3 = Moderate, 4 = Severe. Half (0.5) increments may be used.

The scale values for the study eye will be summarized using continuous descriptive statistics by visit and eye for each treatment group and all randomized subjects. A subject listing of conjunctival redness results will also be produced.

13.1.6 OCULAR SURFACE DISEASE INDEX (OSDI)

Ocular Surface Disease Index (OSDI[©]) includes the following questions:

- 1. Eyes that are sensitive to light?
- 2. Eyes that feel gritty?
- 3. Painful or sore eyes?
- 4. Blurred vision?
- 5. Poor vision?
- 6. Reading?
- 7. Driving at night?
- 8. Working with a computer or bank machine (ATM)?
- 9. Watching TV?
- 10. Windy conditions?
- 11. Places or areas with low humidity (very dry)?
- 12. Areas that are air conditioned?

OSDI[©] will be collected for both eyes at Visits 1, 2, 3, 4 and 5 (pre-CAE). The 5-unit scale for responses to the OSDI[©] is given by the following: 0 = None of the time, 1 = Some of the time, 2 = Half of the time, 3 = Most of the time, and 4 = All of the time. The total OSDI[©] score is calculated by the following:

Note that the number of questions answered in the denominator should exclude those questions with a response of "N/A." Continuous descriptive statistics, including 95% CIs, as well as changes from baseline will be summarized by treatment group as well as between treatment groups. All categorical safety assessments will be summarized by treatment and time point (as applicable) using discrete summary statistics. A subject listing of OSDI® results will also be produced.

13.1.7 UNANESTHETIZED SCHIRMER'S TEST

Subjects' will have the length of the moistened area from the sterile Tear Flo Schirmer strip assessed in each eye at Visits 3, 4, and 5. The Schirmer's test strip will be placed in the lower temporal lid margin of each eye. After 5 minutes, the test strip will be removed, and the length of the moistened area will be recorded in millimeters (mm) for each eye.

The length values for the study eye will be summarized using continuous descriptive statistics by visit and eye for each treatment group and for all actively treated subjects. A subject listing of Schirmer's test results will also be produced.

13.1.8 OCULAR DISCOMFORT DURING CAE

Ocular discomfort scores will be subjectively graded by the subjects according to the following Ora Calibra® Ocular Discomfort Scale for Dry Eye, rating each eye separately, where: 0 = No discomfort, 1 = Intermittent awareness, 2 = Constant awareness, 3 = Intermittent discomfort, 4 = Constant discomfort. The procedure will occur during the 90 minute CAE exposure, starting at time 0 and then every 5 minutes thereafter.

Ocular discomfort scores at Visits 4 and 5 for the study eye will be summarized using continuous descriptive statistics by visit and eye for each treatment group and for all actively treated subjects. A subject listing of ocular discomfort scores will also be produced.

13.1.9 DAILY DIARY SYMPTOM SCORE

Subjects will be asked to complete a dosing diary daily between Visit 1 and Visit 5. The diary symptom scores will be summarized using continuous descriptive statistics for each treatment group and for all actively treated subjects, for the following windows: Day -14 to Day 0, Day 1 to Day 7, Day 8 to Day 14, Day 15 to Day 28, Day 29 to Day 42, Day 43 to Day 63, Day 64 to Day 85. A subject listing will be provided for daily dosing diary records.

13.2 Sensitivity Analysis of Efficacy Variable(s)

Sensitivity analyses will not be conducted for efficacy variables.

14. Safety Analyses

All safety analyses will be conducted using the Safety Population.

14.1 Adverse Events

Treatment-emergent adverse events (TEAEs) are defined as any event that occurs or worsens on or after the first dose of study drug administration. Only TEAEs will be summarized, however all AEs collected in the eCRF will be presented in data listings. All AEs will be coded using the Medical Dictionary for Regulatory Activities (MedDRA), Version 26.1.

An overall summary will be presented that includes the number of events and the number and percentage of subjects who experienced at least one TEAE, by treatment group. This summary will also include breakdowns of TEAEs further categorized as ocular (study eye and fellow eye separately) or non-ocular, treatment-related TEAEs, treatment-emergent serious adverse events (TE-SAEs), TEAEs leading to early treatment discontinuation, TEAEs leading to death, and TEAEs by maximum severity.

Additional summaries of TEAEs will be provided showing the number and percentage of subjects who experienced at least one TEAE by treatment group and classified by the MedDRA SOC and PT. Ocular and non-ocular TEAEs will be summarized separately. If a subject reports multiple TEAEs to the same SOC or multiple PTs within the same SOC, the subject will be counted only once within that SOC or PT. In the summaries, SOCs will be listed in ascending alphabetical order; PTs will be listed in order of descending frequency for all subjects within each SOC.

Separate summaries by SOC and PT will be provided for the following categories of AEs:

- Ocular TEAEs
- Non-ocular TEAEs
- Treatment-related ocular TEAEs
- Treatment-related non-ocular TEAEs
- TE-SAEs

Summaries of TEAEs by maximum severity will be presented for ocular AEs and non-ocular TEAEs separately. The number of subjects with any TEAEs (along with percentages) will be tabulated by SOC and PT within each SOC by treatment group. To count the number of subjects with any TEAEs, if a subject has multiple TEAEs coded to the same SOC or PT within an SOC, the subject will be counted once under the maximum severity.

All AEs will be presented in a subject listing. In addition, SAEs and AEs leading to study treatment discontinuation will be listed separately.

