10.4.6 Safety Variables

Adverse events will be coded using the Medical Dictionary for Regulatory Activities (MedDRA) dictionary. Frequencies and percentages will be provided per treatment group of subjects with treatment-emergent adverse events (TEAEs), serious TEAEs, and TEAEs causing premature discontinuation will be provided by treatment group. An adverse event is treatment emergent if it occurs or worsens after the first dose of randomized study treatment. Furthermore, frequencies will be given of subjects with TEAEs by system organ class and preferred term, by system organ class, preferred term and maximal severity, by system organ class and preferred term for treatment-related adverse events (AEs), by system organ class and preferred term for serious adverse events (SAEs); and by system organ class, preferred term, and day of onset. Separate analyses will be performed for ocular and non-ocular adverse events.

The incidence of patients who experience a TEAE of interest over the 12-week posttreatment observation period will be compared between the IC265 and placebo groups. A generalized linear model will be used, and the distribution will be specified as binomial. The incidence of patients who experience a composite of one or more MedDRA preferred terms of interest over the 12-week post-treatment observation period will be compared between the IC265 and placebo groups. A generalized linear model will be used.

Other safety endpoints will be summarized by treatment and visit using descriptive statistics. Change or shift from baseline will also be summarized where appropriate. For assessments performed by eye, both eyes will be summarized separately.

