| MedDRA | Medical Dictionary for Regulatory Activities |
| MI | Multiple Imputation |
| NCS | Not Clinically Significant |
| QD | Quaque die (Once Daily) |
| PDF | Portable Document Format |
| PP | Per Protocol |
| PT | Preferred Term |
| RDC | Remote Data Capture |
| RTF | Rich Text Format |
| SAE | Serious Adverse Event |
| SAP | Statistical Analysis Plan |
| SD | Standard Deviation |
| SDC | Statistics & Data Corporation |
| SDTM | Study Data Tabulation Model |
| SOC | System Organ Class |
| TEAE | Treatment-Emergent Adverse Event |
| VA | Visual Acuity |
| WHODrug | World Health Organization Drug Dictionary |

1. Introduction

The purpose of this statistical analysis plan (SAP) is to describe in detail the planned analyses and reporting for protocol 23-110-0002, Version 3.0 dated 22AUG2023. The statistical analysis methods presented in this document will supersede the statistical analysis methods described in the clinical protocol. If additional analyses are required to supplement the planned analyses described in this SAP, they may be completed and will be identified in the clinical study report.

This SAP is being written with due consideration of the recommendations outlined in the most recent International Conference on Harmonisation (ICH) E9 Guideline entitled Guidance for Industry: Statistical Principles for Clinical Trials and the most recent ICH E3 Guideline entitled Guidance for Industry: Structure and Content of Clinical Study Reports.

The decision to terminate protocol 23-110-0002 was determined 16NOV2023 due to the emergent adverse events of Epithelial Haziness. Details on how the termination affected the protocol-state analyses can be found in Section 17.

2. Study Objectives

The objective of this study is to compare the safety and efficacy of IC265 Ophthalmic Solution 1% to placebo for the treatment of the signs and symptoms of dry eye disease.

3. Study Endpoints

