4.1 General Study Design

This is a Phase 2, single-center, double-masked, randomized, placebo-controlled clinical study. Subjects will be randomized to one of the following treatment arms at Visit 2 (Day 1):

- IC265 Ophthalmic Solution 1%: 1 drop BID bilaterally (N=~20)
- Placebo Ophthalmic Solution (Vehicle): 1 drop BID bilaterally (N=~20)

Approximately 40 subjects will be randomly assigned to one of the two groups (1:1) to receive either IC265 Ophthalmic Solution 1% or placebo solution as topical ophthalmic drops administered bilaterally BID for 12 weeks. Subjects, Sponsor, Contract Research Organization (CRO), and site personnel will be masked to treatment assignment.

During the 14-day study run-in period prior to randomization, all subjects will receive Placebo Ophthalmic Solution (Vehicle) bilaterally BID.

During the screening period, two 90-minute exposures to the CAE will be conducted to ascertain eligibility to enter the study at Visit 1 (Day -14 \pm 2) and Visit 2 (Day 1). Subjects who qualify after the initial screening visit will enter the run-in phase, where they will self-administer vehicle BID for approximately 14 days. Those who qualify at Visit 2 (Day 1) will be randomized to receive study drug in a double-masked fashion for 84 days. Subjects will self-administer drops BID and will complete Daily diary symptom score assessments as instructed. The CAE exposure will occur at Visit 1 (Day -14 \pm 2), Visit 2 (Day 1), Visit 3 (Day 15 \pm 2), Visit 4 (Day 43 \pm 2), and Visit 5 (Day 85 \pm 4), with Pre-CAE, during CAE and Post-CAE assessments of ocular signs and symptoms. Study drug will be discontinued at Visit 5. Subjects will exit from the study at this visit.

Study visits will be referred to in all tables and listings as the scheduled visit name and planned study day corresponding to the visit to enable reviewers to understand the assessment timing without referring to the protocol visit schedule.

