23.1 Appendix 1: Schedule of Visits and Measurements

| Procedure | | Visit 1 Day -14 ± 2 | | Visit 2 Day 1 | | Visit 3 Day 15 ± 2 | | Day 29 ± 2 | Visit 4 Day 43 ± 2 | | Day 64 ± 2 | Visit 5 Day 85 ± 4/Early Termination | |
|---|------------------|------------------------|---|------------------|---------------|-----------------------|--------------|---------------|-----------------------|--------------|---------------|--|----------|
| | Pre- CAE | Post - CAE | | Post- CAE | Phone Call | | Post- CAE | Phone Call | ı | Post- CAE | Phone Call | Pre-CAE | Post-CAE |
| Informed Consent / HIPAA | X | | | | | | | | | | | | |
| Medical / Medication History and Demographic | X | | | | | | | | | | | | |
| Run-in Collection | | | X | | | | | | | | | | |
| Study drug Collection | | | | | | X | | | X | | | X | |
| Eyecup Phone and/or Diary Collection | | | X | | | X | | | X | | | X | |
| Medical / Medication History Update | | | X | | | Х | | | X | | | X | |
| Adverse Event Query | X | | X | | Х | Х | | X | X | | X | X | |
| Pregnancy Test | \mathbf{X}^{1} | | | | | | | | | | | \mathbf{X}^{1} | |
| Physical Exam (HEENT) | | | X | | | | | | | | | | |
| Ora Calibra™ Ocular Discomfort & 4-Symptom Questionnaire | Х | Х | X | Х | | X | X | | X | X | | X | Х |
| OSDI [©] Questionnaire | X | | X | | | X | | | X | | | X | |
| Visual Analog Scale (VAS) | X | | X | | | X | | | X | | | X | |
| y (Visual Acuity (ETDRS) | X | | X | | | X | | | X | | | X | |
| Review of Qualification Criteria | X | X | X | X | | | | | | | | | |
| Slit-lamp Biomicroscopy | X | X | X | X | | X | X | | X | Х | | X | X |

| TFBUT | X | X | X | X | | X | X | X | X | X | X |
|--|----------|-------|---|-------|---|-------|---|-------|---|-------|---|
| Fluorescein Staining | X | X | X | X | | X | X | X | X | X | X |
| Lissamine Green Staining | X | X | X | X | | X | X | X | X | X | X |
| Conjunctival Redness | X | X | X | X | | X | X | X | X | X | X |
| CAE® Exposure | 2 | X | | X | | X | | X | | X | |
| Ora Calibra™ Ocular Discomfort Scale | X | X^2 | |
| Digital Photography* | X | X | X | X | | X | X | X | X | X | X |
| Unanesthetized Schirmer's Test | X | | X | | | X | | X | | X | |
| Intraocular Pressure | | X | | | | | | | | | X |
| Undilated Fundus Exam | | X | | | | | | | | | X |
| Run-in Article Dispensation | | Х | | | | | | | | | |
| Run-in Instillation | | X | | | | | | | | | |
| Randomization | | | | X | | | | | | | |
| Randomized Study Drug Instillation | | | | X | | | X | | X | | |

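### The adverse-event tables give counts and percentages for epithelial haziness, the event that stopped the trial, but no detection timing, time at risk or interval on the arm difference, and the Day 85 slit-lamp row may mix in much earlier exams

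*SAP*

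**What the plan says.** **Why the trial stopped.** SAP 1 says the decision of 16 November 2023 was taken "due to the emergent adverse events of Epithelial Haziness". SAP 17 then drops statistical testing and keeps descriptive statistics.

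**Adverse events.** SAP 14.1 plans the "number and percentage of subjects who experienced at least one TEAE by treatment group and classified by the MedDRA SOC and PT". It adds event counts, study and fellow eye, relatedness, seriousness, events leading to discontinuation, and maximum severity. Tables 14.3.1.1 to 14.3.1.6 in SAP 20 contain no onset, exposure-linked or risk-difference table. Exposure is summarized by arm in its own table (SAP 12.2).

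**Corneal examination.** SAP 14.3 tabulates slit-lamp results by visit, arm and eye, with shifts from baseline. The cornea is graded normal, abnormal NCS or abnormal CS.

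**Visit labels.** SAP 4.1: "Study visits will be referred to in all tables and listings as the scheduled visit name and planned study day corresponding to the visit". The schedule in SAP Appendix 1 has one column headed "Visit 5 Day 85 ± 4/Early Termination". The SAP gives no rule for placing early-termination or unscheduled exams.

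**Protocol.** Section 10.4.6 of protocol V1.0 lists TEAE frequencies "by system organ class, preferred term, and day of onset". It also plans an arm comparison of "The incidence of patients who experience a TEAE of interest over the 12-week posttreatment observation period". The SAP, however, is written for "protocol 23-110-0002, Version 3.0 dated 22AUG2023", which is not among the documents supplied.

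**Extra analyses.** SAP 1 says of analyses beyond those planned that "they may be completed and will be identified in the clinical study report".

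**The concern.** Once a trial has been stopped for a corneal event, its main remaining safety questions are how often the event occurs, how soon, and with what excess over vehicle. A row of subjects and percentages answers only the first, and only for the follow-up each subject happened to have.

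Two things are at stake. First, where follow-up was cut short, the crude percentage need not equal a risk over 12 weeks, and the tables do not let a reader see the difference. Second, the same row fits both onset confined to the first weeks and onset that continues with dosing.

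The slit-lamp tables could fill part of this gap, but the stop itself undermines their last row. Protocol 5.5 asks that subjects leaving early complete the Visit 5 exit procedures. With a shared column and planned-day labels, an exam done around Day 43 could be reported as Day 85.

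**Working it through.** The plan states no event rate, power or risk figure to reproduce. The check compares the documents, then uses illustrations whose counts and follow-up are **assumed**.

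**1. Follow-up at the stop (dates from the documents).**
- Protocol V3.0 is dated 22 August 2023; the stop was decided on 16 November 2023, 86 days later.
- Screened on 22 August with a 12-day run-in: Day 1 is 3 September and 16 November is Day 75. Visit 5 opens on Day 81 (85 − 4), so the last scheduled exam reached is Visit 4.
- Screened on 10 August with a 14-day run-in: Day 1 is 24 August and 16 November is Day 85, so follow-up is complete.
- V1.0 is dated 12 June 2023, 157 days before the stop.

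The documents do not say when anyone was screened. Both cases are possible and the truncated share is unknown.

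**2. Resolution of timing.** Nominal gaps between scheduled exams are 15 − 1 = 14, 43 − 15 = 28 and 85 − 43 = 42 days. Within windows they can reach 17 − 1 = 16, 45 − 13 = 32 and 89 − 41 = 48 days. Between them there are only telephone queries on Days 8, 29 and 64. The onset date of a corneal sign is therefore largely a detection date.

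**3. What a pooled Day 85 row could hold.** Assume 20 exams in the row, 10 on Day 85 and 10 early-termination exams on Day 43. The mean actual day is (10 × 85 + 10 × 43)/20 = 64.

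**4. Crude percentage against 12-week risk.** Assume a share *s* of subjects stops on Day 43 (6 weeks), the rest complete 12 weeks, and the hazard is constant with 12-week risk *R*:

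crude = (1 − s)R + s[1 − (1 − R)^(6/12)]

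| R | s = 0 | s = 0.25 | s = 0.50 | s = 1 |
|---|---|---|---|---|
| 40% | 40.0 | 35.6 | 31.3 | 22.5 |
| 20% | 20.0 | 17.6 | 15.3 | 10.6 |

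If all onset falls in the first two weeks, nothing is lost. At R = 40% the understatement runs from nil to 40.0 − 22.5 = 17.5 points.

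**5. Two patterns, one adverse-event row.** This is a separate illustration with full follow-up to Day 85: 20 subjects, 5 events, intervals of 2, 4 and 6 weeks, subjects leaving the risk set after detection. Both patterns print as 5/20 (25.0%). Rates are per 100 subject-weeks with exact Poisson 95% limits.

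| Detections | Subject-weeks | Rate, interval 1 | Rate, interval 2 | Rate, interval 3 | Pooled |
|---|---|---|---|---|---|
| 4, 1, 0 | 40, 64, 90 | 10.0 (2.7–25.6) | 1.6 (0.04–8.7) | 0 (0–4.1) | 5/194 = 2.6 |
| 1, 2, 2 | 40, 76, 102 | 2.5 (0.06–13.9) | 2.6 (0.3–9.5) | 2.0 (0.2–7.1) | 5/218 = 2.3 |

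A single pooled rate also hides the difference, so rates should be given by interval.

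**6. Precision of the arm difference.** Newcombe 95% intervals at 20 per arm: 4 vs 0 is 20 points (−0.1 to 41.6); 5 vs 0 is 25 points (3.8 to 46.9).

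**The case against.** **Much is already planned.** A reader might infer that haziness appears only as a percentage by SOC and PT. The documents do not support that: SAP 14.1 has several further cuts, and SAP 14.3 tabulates the cornea by visit, arm and eye. If the corneal grade followed the event, the two patterns in step 5 would usually look different at Visit 3. This stands as a limit on the point. What remains is that the grade does not name haziness, carries no count of subjects still free of the event, and has a last row of uncertain date.

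**The listings show dates.** Protocol 9.1 requires an onset date, and with about 40 subjects planned the listings can be read by hand. However, the SAP does not specify the listing columns, and a listing is not a summary by arm with a denominator.

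**Truncation may be trivial.** It may. Disposition and exposure are shown by arm, and the SAP never calls its percentage a 12-week risk. A reader might also infer that the stop biases the arm comparison. Nothing supports that: a calendar stop is unrelated to randomized arm and does not by itself favour either.

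**The study is exploratory and descriptive.** True, but an interval is not a test. SAP 13.1.6 keeps 95% CIs within and between arms for OSDI. That is only a modest precedent, because OSDI is a continuous score. SAP 1 permits extra analyses but does not commit to these.

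**Conclusion.** The point holds. The planned counts are not wrong. They leave out timing of first detection, time at risk, and the size of the arm difference with its uncertainty, for the one event that ended the trial. In addition, the Day 85 slit-lamp row has no rule to keep out exams done much earlier.

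The numerical effect is unknown. Depending on onset pattern and truncated share, the gap between the crude percentage and the 12-week risk is nil to 17.5 points at an assumed 40% risk, the upper end requiring a constant hazard and every subject stopping on Day 43. Arm sizes, event counts and truncation are not in the documents.

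A reader might infer that the SAP silently dropped the protocol's day-of-onset table. That cannot be concluded: the table is in V1.0, the SAP follows V3.0, and without V3.0 it cannot be judged whether its absence needed declaring in SAP 17.

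**What to change.** **(a) SAP 14.3 and the by-visit tables.** Do not pool early-termination and unscheduled exams into the Day 85 row. Either assign them by actual study day, using analysis windows that contain the protocol visit windows, or show them in a separate row.

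**(b) SAP 14.1.** Add a descriptive block, labelled post hoc and without p-values, for one grouped epithelial-haziness event. Fix its preferred-term list before unmasking, which under SAP 6.1 follows database lock. Report by arm:
- subjects with the event, and the risk difference with 95% CI;
- first detection by interval, with subjects and subject-time at risk in each. Use intervals that respect the visit windows, for example Day 1–17, Day 18–45 and Day 46–89, and place every finding by its actual date. State that onset of a corneal sign is a detection date.

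**(c) Corneal shift.** Add a subject-level shift of slit-lamp cornea grade from baseline to worst on-treatment value. Show pre-CAE and post-CAE exams separately, each against its matching Visit 2 exam, so that change provoked by the CAE is not mixed in. List unscheduled exams separately.

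**(d) Protocol V3.0.** Check whether it kept the day-of-onset table. If so, restore it or list its removal in SAP 17.

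**Cost.** Two or three extra tables from dates and exposure already collected. Intervals will be wide at about 20 per arm, the event definition is post hoc, and timing can be no finer than the examination schedule.
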